2022-04-14

**FACE TO FACE OR DIGITALLY? A COMPARISON OF FIRST-LINE INTERVENTIONS DELIVERY FOR
PEOPLE WITH HIP OR KNEE OSTEOARTHRITIS (NCT04836988)**

Background

Osteoarthritis (OA) is among the leading causes of disability worldwide and due to its raising prevalence, the identification of appropriate care and care delivery modalities is a priority for the health care systems [1, 2]. Exercise and education constitute the first-line intervention for people with knee and hip OA and have been shown to be effective regardless of symptoms and disease severity [3, 4]. Unfortunately, there is a discrepancy between recommended treatment and what patients receive. Less than 40% of people with OA seeking care seem to receive recommended first line management internationally [5]. To implement those guidelines, the Better Management of Patients with OsteoArthritis (BOA), a face-to-face concept including education and an option to exercise, has been developed and are offered at primary care clinics in Sweden since 2008 [6]. However, traditional face to face interventions present barriers, such as limited access and lack of flexibility, which may limit the patients' adherence with the interventions [7]. Digital delivery of the management program may be one way of overcoming such barriers [8, 9]. In light of the current Covid-19 pandemic, digitally delivered treatments may gain even further awareness as a feasible treatment option. Both delivery methods have been reported to reduce OA symptoms in patients with hip and/or knee OA [10, 11], but little is known whether the results of digital interventions are comparable with traditional face-to-face rehabilitation programs.

Aim

To compare the outcomes (average treatment effect) of two different modalities of first-line treatment delivery (face-to-face vs. digitally) after 3 months of program participation.

Hypothesis

There will be no difference in the average treatment effect of the main outcome between the two delivery methods.

Methods

This is a retrospective observational registry-based study comparing outcomes of a face-to-face and a digital OA management program.

The study was approved by the regional ethics committee of the Swedish Ethical Review Authority (Dnr 2019-06288, decision date 2020-02-11 and is pre-registered at ClinicalTrials.gov (NCT04836988). Participants were informed that data generated from the register may be used for research purposes at registration (BOA) or provided digital informed consent for the same purpose at registration (JA). The study adheres to the STROBE guidelines for observational studies.

Data sources

BOA (face-to-face): The BOA registry was started in 2008 and currently includes more than 100,000 individuals with OA who have registered for an evidence-based self-management program, including education, exercise and weigh management if needed at a primary care clinic.

Joint Academy (digital program): The digital self-management program started in 2014 and was originally inspired by the Swedish evidence based face-to-face BOA self-management treatment program [9]. The associated registry currently includes more than 30 000 individuals with OA. The intervention consists of a digital OA self-management program (Joint Academy®) [11, 12] comprising text lectures on OA with accompanying quizzes, physical activity and self-management in OA. The participant also receives exercises aiming at improving strength and neuromuscular control of various levels based on each individuals' progression in the program.

Data extractions and linkages

All data extracted from the digital self-management program (JA) and BOA registries. Criteria for inclusion in the data extraction are:

- Clinical diagnosis of OA, with knee or hip OA as their index (most symptomatic) joint
- Enrolled in either of the two programs between April 1, 2018 and December 31, 2019
- Provided 3-month follow-up data for the main outcome on or before March 31, 2020
- Program adherence of 80% or higher.

The data from the two registers will be linked using personal identity numbers to identify individuals that may have participated in both programs during the specific time window. Patients that participated in both programs will be excluded from further analysis.

The JA participants will be matched 1:1 to participants in the BOA register using the propensity scoring approach described below.

Main exposures and outcomes

Exposures

Three months of first-line OA treatment delivered either face-to-face or digitally with a program adherence of 80% or higher. The choice of this cut-off was based on recommendations in the Swedish Guidelines for management of knee and hip osteoarthritis by the National Board of

Health and Welfare. Adherence defined as $\geq 80\%$ completed education videos, exercises and questionnaires offered in the digital program and participation in two out of three educational lessons and at least 10 of the 12 supervised group exercise sessions offered in the BOA program.

Main outcome

Main outcome will be self-reported change in pain on the NRS-scale between baseline and three months follow-up. The NRS comprises an 11-point scale where 0 indicates no pain and 10 indicates the worst possible pain [13] (Table 1).

Secondary outcomes

Secondary outcomes will be change in self-reported walking difficulties (dichotomous reply, yes/no), willingness for joint surgery (dichotomous reply, yes/no) and health-related quality of life, assessed with the EuroQol – 5 dimension descriptive system (EQ-5D-3L)[14] between baseline and three months follow-up (Table 1).

Sample size

As this study aims at estimating treatment effects, the important issue to assess is not power (related to a hypothesis), but precision – i.e. the width of the confidence interval. To illustrate this, consider the example of an RCT to compare mean joint pain after exercise intervention for OA, between persons that receive the treatment in different modalities. The minimum clinically important difference is typically considered one unit on a 0-10 NRS scale. To obtain a 95% confidence interval for the between-group difference with a width of at most 0.5 units (i.e. very precise) in a sample with a typical standard deviation of 1.5, with 99% probability, we will need ~ 630 patients in total. Considering our cohort size of >2000 persons who underwent the intervention, we will be able to estimate between-group differences also in subgroups, by sex, BMI, etc.

Statistical analysis

In this study we will use observational data to emulate an equivalence trial comparing the effect on joint pain of a digitally delivered first-line intervention and of an in-person delivered first line intervention for people with OA of the hip or knee.

Main outcome analysis

The main outcome will be analyzed using a propensity score matching approach [17]. We will estimate the propensity score using a logistic regression model, in which we will regress the treatment status on the observed baseline characteristics of the participants. The characteristics to include in the propensity score will be selected using the disjunctive cause

criteria [16], including factors in the analysis identified as causes of treatment allocation(exposure) and/or the pain change (outcome) (Table 2). We will use nearest neighbor matching to select controls (BOA participants) whose propensity score is closest to that of the treated subject. Furthermore, we will use an optimal matching strategy to minimize the total within-pair difference of the propensity score. Within-pair differences in main outcome will be analysed using a paired t-test. Finally, we will adjust the analysis for baseline pain using linear regression in order to increase the precision of the estimates and minimize the regression to the mean effect [17, 18].

Assessing propensity score balance

Balance of baseline variables between treated and control subjects in the matched study population will be assessed using standardized difference [19].

Equivalence bounds

In order to establish equivalence between the interventions the pain change after the intervention should differ of less than 1-point on a 0-10 NRS pain scale. This cut off was selected based on previous work identifying 1-point change as the MCID in people with OA [20].

Sensitivity analysis

In order to evaluate and contrast the influence of choice of analysis method on study results, linear regression analysis based on the same adjustment set used for the propensity score, representing the causal effect studied, will be applied and both adjusted and unadjusted estimates will be presented, discussed and contrasted against results from the propensity score matched analysis.

Missing data

Data on study drop-outs will be summarized by treatment group using frequency counts to assess any imbalance. If the fraction of missing study data is non-ignorable (i.e. 5% or more with missing data in either outcome and/or any adjustment variable), then multiple imputation techniques, such as MICE [21] will be applied to the analysis of the primary outcome. The analysis method will also be altered to a linear regression approach, as opposed to that of propensity score matching, in order to facilitate incorporation of missing data methods in the analysis procedure. However, when the fraction of missing data is small (i.e. 5% or more with missing data in either outcome and/or any adjustment variable), the primary analysis will be performed using a complete case approach.

References

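### A returned 3-month pain score is a condition of extraction, so the SAP's 5% missing-data rule cannot respond to non-response, and both branches of that rule carry the same threshold

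*SAP*

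**What the plan says.** Under Data extractions and linkages, one criterion for entering the data set is that the person "Provided 3-month follow-up data for the main outcome on or before March 31, 2020". Program adherence of at least 80% is a further criterion.

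The Exposures section defines the exposure as "Three months of first-line OA treatment delivered either face-to-face or digitally with a program adherence of 80% or higher". It justifies the 80% cut-off by national guidelines. For the digital program, adherence counts videos, exercises and questionnaires. For the face-to-face program (BOA), it counts attendance at lessons and exercise sessions only.

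Under Missing data, the SAP states: "Data on study drop-outs will be summarized by treatment group using frequency counts to assess any imbalance". Two branches follow. The first reads "If the fraction of missing study data is non-ignorable (i.e. 5% or more with missing data in either outcome and/or any adjustment variable" and leads to multiple imputation; with it, "The analysis method will also be altered to a linear regression approach, as opposed to that of propensity score matching". The second applies "when the fraction of missing data is small (i.e. 5% or more with missing data in either outcome and/or any adjustment variable" and leads to a complete-case analysis.

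The one sensitivity analysis is a "linear regression analysis based on the same adjustment set used for the propensity score". For equivalence, "the pain change after the intervention should differ of less than 1-point on a 0-10 NRS pain scale".

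**The concern.** The missing-data rule is meant to protect the primary analysis against incomplete outcomes, but the extraction criterion removes incomplete outcomes before the rule is applied. The pain outcome at 3 months will look complete whatever share of each program's participants failed to answer. A returned score is also a condition over and above adherence. The SAP justifies the adherence restriction, but gives no reason for restricting to responders.

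If response differs between programs, or is related to improvement differently in each, the comparison of responders can differ from the comparison of all adherers. No planned analysis addresses that.

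The duplicated threshold is a separate fault with a direct consequence. The rule chooses between propensity-score matching on complete cases and imputation with linear regression, so an ambiguous rule leaves the primary method undetermined.

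**Working it through.** **1. Can non-response trigger the rule?** Take N otherwise eligible people, a fraction m of whom have no 3-month score. The extraction keeps N(1 − m), all with a score, so the missing share of 3-month pain in the extract is 0 / [N(1 − m)] = 0. With N = 1000 and assumed m of 5%, 20% and 50%, the extract holds 950, 800 and 500 people, and the missing share is 0% each time. Before extraction every one of these rates meets the 5% threshold; after it, none does.

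The rule is not wholly inert. Baseline pain is needed for the change score and is a matching variable, and it or any other adjustment variable may be missing.

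**2. Which branch applies?** Reading the two conditions literally:

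- 5% or more missing: imputation with regression applies, and so does complete-case analysis.
- Less than 5% missing: neither applies.

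**3. Does another analysis fill the gap?** The sensitivity analysis replaces matching by regression on the same adjustment set. It draws on the same extraction, so it holds the selection on response constant.

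**4. Is the selection the same in both arms?** Questionnaire completion counts towards adherence in the digital program only. The SAP does not say whether the 3-month form is among those questionnaires. If it is, the adherence criterion itself adds response-linked selection in the digital arm.

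**5. How large might the effect be?** The SAP gives no response rates, so every rate, gap and correlation below is assumed.

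*Random error, for scale.* The SAP's own precision figure reproduces. The smallest n per arm with P(t(0.975, 2n − 2) × s × √(2/n) ≤ 0.25) ≥ 0.99 at SD 1.5 is 316, or 632 in total against about 630 stated. That figure is unaffected by this point. If 2000 people were analysed 1:1, the 95% CI half-width would be about 1.96 × 1.5 × √(2/1000) = 0.13, treating the groups as independent.

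*Direct gap.* Within an arm, the responder mean minus the mean of all adherers is m × d, where d is the responder minus non-responder difference in improvement. With the same d in both arms, the between-program shift is (m₁ − m₂) × d:

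- 20% vs 20%, d = 1: 0
- 40% vs 20%, d = 1: 0.2
- 50% vs 20%, d = 1: 0.3
- 50% vs 20%, d = 2: 0.6

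*Latent-normal response model.* Let r be the correlation between improvement and a normally distributed latent tendency to respond (not the yes/no response itself). The shift is SD_res × r × [λ(p_low) − λ(p_high)], with λ(p) = φ(z_p)/p, where p is the response rate. This gives λ(0.95) = 0.109, λ(0.90) = 0.195, λ(0.80) = 0.350, λ(0.70) = 0.497 and λ(0.50) = 0.798. Take r from 0.1 to 0.3 and residual SD from 1.06 (half the variance explained) to 1.5:

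- 95% vs 80% response: 0.241 × SD_res × r = 0.03 to 0.11
- 90% vs 70%: 0.302 × SD_res × r = 0.03 to 0.14
- 90% vs 50%: 0.603 × SD_res × r = 0.06 to 0.27
- 70% in both, r = 0.1 in one and 0.3 in the other: 0.2 × 0.497 × SD_res = 0.11 to 0.15

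To connect the two models: at 50% response, SD 1.5 and r = 0.3, the implied responder gap is 0.798 × 1.5 × 0.3 / 0.5 = 0.72. The 2-point gap in the first list is therefore a much harsher assumption.

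**The case against.** **Drop-outs may be counted from the registers.** A reader might infer that differential non-response would stay invisible. The document does not support that. A drop-out summary by group is planned and STROBE reporting is promised, so counts may well come from the full registers. Their unstated source is missing detail, not an error. What stands is that such counts would describe non-response without any analysis acting on it.

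**Adherence is part of the declared exposure.** This is correct. A reader might infer that the SAP should analyse everyone enrolled, but that answers a different question from the exposure it defines and justifies, so it is not required here. Nor is returning a questionnaire wholly separate from the exposure, since questionnaires count towards digital adherence.

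**The second threshold is an evident slip.** The contrast between a non-ignorable and a small fraction makes less than 5% the likely intent. That makes the correction easy, but a rule that selects the primary method should not depend on the reader's repair.

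**The bias is speculative and small against the bound.** This stands. A reader might infer that the equivalence conclusion is unsafe. No response rate in the document supports that, and the relevant rates are those among adherers.

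**Conclusion.** The point holds as an inconsistency between the extraction criterion and the missing-data rule, plus a wrong threshold in that rule. Both follow from the text alone and need no assumption about response rates. It should be fixed, but it does not show that the result is biased.

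The size and direction of any bias are unknown. Under the latent-normal assumptions the shift is 0.03 to 0.27 NRS points where response rates differ. It is zero when both response and its relation to improvement are equal across programs. The larger values match or exceed a random error of about 0.13, yet remain well below the 1-point bound. Even the harshest assumed case, 0.6, would not by itself break equivalence if the true difference were zero: 0.6 + 0.13 = 0.73. It could matter only if added to a real difference between programs. As planned, the result is a comparison of adherent responders and should be described that way.

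**What to change.** 1. **Missing data:** change the complete-case threshold to less than 5%.
2. **Data extractions and linkages:** move the returned-score condition from extraction to the definition of the complete-case analysis set, so that people who meet the diagnosis and enrolment-window criteria are extracted with or without a 3-month score.
3. **Missing data:** report enrolled, at-least-80%-adherent and followed-up counts, with baseline characteristics, by program from that extraction. Show separately those whose 3-month date falls at or near 31 March 2020. Enrolment runs to 31 December 2019, exactly three months before the cut, so a slightly late reply from a late enrollee would otherwise be counted as non-response.
4. **Main outcome and sensitivity analyses:** keep the matched comparison among adherent responders as primary and label it so. Add one sensitivity analysis among adherers that handles missing 3-month pain by multiple imputation or inverse-probability-of-follow-up weights. State that missing 3-month scores do not trigger the switch away from matching.
5. **Exposures:** state whether the 3-month questionnaire counts towards digital adherence.

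The cost is a wider extraction from the same two registers, a flow table, one more analysis and a few wording changes. The SAP does not show whether a wider extraction is still possible. If it is not, counts by program from the registers and the corrected threshold are the minimum. Imputation or weighting will not remove selection on unmeasured factors.

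### The both-programmes exclusion has no timing rule: it can drop people who switched after giving a clean 3-month outcome, and it cannot see use of the other programme before the window

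*SAP*

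**What the plan says.** All of the following stands in the SAP under Data sources and Data extractions and linkages, unless another section is named.

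- Eligibility by date: "Enrolled in either of the two programs between April 1, 2018 and December 31, 2019".
- Outcome by date: "Provided 3-month follow-up data for the main outcome on or before March 31, 2020". Programme adherence of at least 80% is also required.
- Linkage: the registers are "linked using personal identity numbers to identify individuals that may have participated in both programs during the specific time window".
- Exclusion: "Patients that participated in both programs will be excluded from further analysis".
- Register history: "The BOA registry was started in 2008" and "The digital self-management program started in 2014".

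The section Main exposures and outcomes defines exposure as three months of one delivery mode and the main outcome as change in NRS pain from baseline to three months. Earlier use of the other programme is neither an eligibility criterion nor a variable in Table 1. The only sensitivity analysis described is linear regression on the same adjustment set as the propensity score.

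**The concern.** The exclusion does not say whether the second programme must overlap the first, or start before its outcome is measured. Two consequences follow.

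First, someone who completed one programme, reported pain at three months and only then joined the other has an uncontaminated exposure and outcome, yet the rule removes them. The SAP sets out to emulate an equivalence trial, and a trial would not discard a participant for something done after the endpoint was recorded. If people tend to switch because pain did not improve, the removed group is enriched for poor responders, and the retained mean in that arm is too favourable. A propensity score built on baseline variables cannot undo this.

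Second, the check reaches only as far as the window. A person who took one programme before April 2018 and the other inside the window stays in the cohort. Earlier use plausibly affects both the choice of programme and the response to it, which is the kind of factor that the SAP's covariate selection rule is meant to capture.

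**Working it through.** **1. The plan's own figure.** The Sample size section asks for a 95% interval of full width at most 0.5 with SD 1.5 and 99% probability, and gives about 630 in total. For a two-sample t interval, the requirement is P(2 × t(0.975, 2n−2) × s × √(2/n) ≤ 0.5) ≥ 0.99. The smallest n is 316 per arm, 632 in total (probability 0.991). At 315 per arm the probability is 0.989. The stated figure reproduces, and this point does not alter it.

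**2. Precision at the expected cohort.** The SAP expects more than 2000 people. With 1000 per arm, the half-width is 1.96 × 1.5 × √(2/1000) = 0.13. With 99% assurance the full width is 0.273, so the half-width is about 0.14.

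**3. Time at risk of removal after a complete outcome.** This reads the linkage window as the enrolment window, 1 April 2018 to 31 December 2019 (21 months).
- Enrolled 1 April 2018: outcome about 1 July 2018, leaving 549 days (about 18 months) in which a later enrolment removes the person.
- Enrolled in the last three months of the window: none.
- If entry is uniform, 18/21 = 86% of enrolees have some such time. The mean over all enrolees is (18 × 18/2)/21 = 7.7 months.

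**4. Size of the selection shift.** The SAP gives no switching share and no pain results for switchers, so these inputs are assumptions. Let p be the share of one arm removed after the outcome, and d the amount by which their improvement falls short of that arm's full mean. The retained mean then shifts by p × d/(1 − p).

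| p | d = 0.5 | d = 1.0 | d = 2.0 |
|---|---|---|---|
| 1% | 0.005 | 0.010 | 0.020 |
| 5% | 0.026 | 0.053 | 0.105 |
| 10% | 0.056 | 0.111 | 0.222 |

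The between-arm contrast is affected only by the difference between the two arms' shifts. With p = 5% in both arms and equal d it is zero. With 5% against 1% and d = 1.0 it is 0.053 − 0.010 = 0.043.

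**5. Size of the carry-over shift.** Let c be the share of one arm with earlier use of the other programme, and a the reduction in their response. The shift is c × a. For c from 1% to 20% and a from 0.5 to 1.5 points it runs from 0.01 × 0.5 = 0.005 to 0.20 × 1.5 = 0.30. Both inputs are assumed, and matching on baseline status would absorb part of the effect.

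**The case against.** Excluding dual participants is a common way to keep a comparison clean, and several counter-arguments carry weight.

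- **Selection on the result is not shown.** A reader might infer that the rule removes non-responders and flatters the programme that people leave more often. The SAP supports neither. It gives no count of dual participants, no reasons for switching and no split by arm. The rule conditions on a later enrolment. That becomes selection on the outcome only if switching depends on pain response, and it biases the contrast only if the effect differs by arm. This limit stands.
- **The number caught may be small.** The linkage sentence follows directly after the extraction criteria. If only the filtered extracts are linked, a switcher is found only after also reaching 80% adherence and giving a 3-month outcome in the second programme. Fewer late switchers would then be lost, but people who used part of the other programme inside the window would go unnoticed. The SAP does not say which reading applies, and that needs settling in either case.
- **Baseline matching covers part of the carry-over.** Table 1 matches on baseline pain, physical activity, fear of movement, wish for surgery, walking difficulties and overall health. Only the effect of earlier use that does not pass through these is left unadjusted. The SAP also points to a Table 2 for the covariate set, which is not in the text at hand. A reader might infer that former face-to-face users fall mainly in the digital arm, because that register is older and larger. This is plausible, but the SAP does not establish it.
- **The equivalence conclusion is unlikely to turn on this.** Even the extreme selection shift plus the half-width, 0.22 + 0.14 = 0.36, lies well inside the 1-point margin. This stands.
- **The narrower rule is not free of conditioning.** Excluding people who start the second programme before the 3-month outcome still conditions on a post-baseline event. That is true, but those people's exposure really is mixed, which is not so for later switchers.

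None of this supplies a timing rule, and nothing else in the SAP repairs its absence.

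**Conclusion.** The point holds in a limited form. As written, the exclusion can remove people with a complete, uncontaminated 3-month exposure and outcome because of an enrolment up to about 18 months later, and the opportunity for removal falls to nothing for the last enrolees. It conditions on a post-outcome event that may depend on pain response, and it biases the contrast if that dependence or the amount of switching differs by arm. The check also misses use of the other programme before the window, which is adjusted for only indirectly.

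The size is unknown. On the assumed inputs the one-arm selection shift is 0.005 to 0.22 points. Its upper part is comparable with or larger than the half-width of 0.13 to 0.14, so it could matter for the precision that the SAP claims, but it is small against the 1-point margin. The timing figures rest on reading the linkage window as the enrolment dates, which the SAP does not spell out. The change is worth making because the rule is easy to put right, not because the equivalence conclusion is shown to be at risk.

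**What to change.** In Data extractions and linkages:

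1. Define exposure as a person's first enrolment in the window.
2. Exclude for dual participation only when the other programme started before the 3-month outcome of that first enrolment. Keep later switchers under their first programme.
3. Give the dates of the linkage window, and state whether linkage uses all enrolments in it or only records that already meet the adherence and outcome criteria.
4. Report the number excluded for dual participation by arm, and run the present rule as a sensitivity analysis.
5. Where data permissions allow, extend the linkage back to the start of each register (2008 and 2014), and exclude or match on earlier use of the other programme.

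Items 1 to 4 cost SAP wording and a slightly changed cohort, and they rely on the identity-number linkage already planned. If that linkage was to run only on filtered extracts, finding partial users needs the unfiltered window enrolments. Item 5 needs a wider extraction of identifiable data than the one planned, and the SAP does not show whether the ethics approval covers it. It should therefore be treated as desirable and not as a condition for the other changes.

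### The aim names an average treatment effect, but the matching estimates an effect over digital users, and the regression that may replace it has no fixed target population

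*SAP*

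**What the plan says.** The Aim is "To compare the outcomes (average treatment effect) of two different modalities of first-line treatment delivery" after three months, and the Hypothesis reads "There will be no difference in the average treatment effect of the main outcome between the two delivery methods". Under Statistical analysis, the study is described as emulating an equivalence trial of a digital intervention and "of an in-person delivered first line intervention for people with OA of the hip or knee".

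Under Data extractions and linkages, the direction of matching is fixed: "The JA participants will be matched 1:1 to participants in the BOA register using the propensity scoring approach described below". Main outcome analysis repeats it, planning to "select controls (BOA participants) whose propensity score is closest to that of the treated subject". The same extraction criteria restrict both groups to programme adherence of 80% or higher and to people who "Provided 3-month follow-up data for the main outcome on or before March 31, 2020".

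Two further regressions matter here.

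- Under Sensitivity analysis, the aim is to evaluate "the influence of choice of analysis method on study results, linear regression analysis based on the same adjustment set used for the propensity score", with its estimates set beside those from matching.
- Under Missing data, if 5% or more is missing in the outcome and/or any adjustment variable, multiple imputation is used and the primary analysis itself moves from matching to linear regression.

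For neither regression does the SAP state the sample, any programme-by-covariate terms, or the population over which the effect is averaged.

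**The concern.** Three analyses are treated as estimates of one quantity, but as written they need not share a target population.

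- Choosing the closest BOA control for each JA participant averages the contrast over the characteristics of digital users (an effect in the treated), provided all of them are closely matched.
- A main-effects linear regression on all eligible participants gives most weight to covariate levels where both programmes are well represented (an overlap-weighted effect).
- An average treatment effect over all eligible participants is a third quantity.

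The three coincide if the effect of delivery mode is constant. They separate if it varies with a covariate whose distribution differs between the programmes.

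Two things are at stake. First, a contrast for digital users would be reported as a general average effect. Second, the target of the primary analysis could change with how much data is missing. Because three-month pain is an inclusion criterion, missing adjustment variables would be the main trigger. The sensitivity regression shares the ambiguity only if it is fitted on all eligible participants. A gap from matching could then reflect different populations, while the SAP would read it as the influence of method.

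**Working it through.** **The plan's own figure.** Sample size gives about 630 patients for a 95% interval of width at most 0.5, SD 1.5, with 99% probability. Without the probability requirement, n per arm = 2 × (1.96 × 1.5 / 0.25)² = 276.6, about 554 in total. With it, the smallest n per arm is 316, or 632 in total. The figure is reproduced, and the point below does not affect it.

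**Inputs for the illustration.** All are assumptions, except that 3.33:1 is the ratio of whole-register sizes in the SAP (more than 100,000 BOA, more than 30,000 JA), before eligibility.

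- One binary effect modifier, present in a share pJ of JA and pB of BOA: 60%/40% or 70%/30%.
- Programme effect 0 at one level and d at the other, in absolute size: d = 0.5 or 1.0 NRS point.
- r = eligible BOA per JA participant, up to 10. Close 1:1 matching of all JA participants without replacement needs r ≥ pJ/pB, that is 0.6/0.4 = 1.5 or 0.7/0.3 = 2.33.

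**Formulas.**

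- Matched (all JA matched): pJ × d.
- Main-effects regression on all eligible: each level is weighted by nJ × nB / (nJ + nB).
- Average over all eligible (ATE): d × (pJ + r × pB) / (1 + r).

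**Worked case: 70/30, r = 3.33, d = 1.0, per JA participant.**

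- Level with the modifier: nJ = 0.70, nB = 0.30 × 3.33 = 1.00; weight 0.70 × 1.00 / 1.70 = 0.412.
- Level without it: nJ = 0.30, nB = 0.70 × 3.33 = 2.33; weight 0.30 × 2.33 / 2.63 = 0.266.
- Regression: 0.412 / (0.412 + 0.266) = 0.608.
- Matched: 0.700. ATE: 1.70 / 4.33 = 0.392.

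| Split, d | r | Matched | Regression | Gap | ATE |
|---|---|---|---|---|---|
| 60/40, 0.5 | 1.5 | 0.300 | 0.260 | 0.040 | 0.240 |
| 60/40, 0.5 | 3.33 | 0.300 | 0.277 | 0.023 | 0.223 |
| 60/40, 0.5 | 10 | 0.300 | 0.291 | 0.009 | 0.209 |
| 70/30, 1.0 | 2.33 | 0.700 | 0.580 | 0.120 | 0.420 |
| 70/30, 1.0 | 3.33 | 0.700 | 0.608 | 0.092 | 0.392 |
| 70/30, 1.0 | 10 | 0.700 | 0.664 | 0.036 | 0.336 |

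All quantities scale with d, and the other two combinations fall inside these ranges. The matched-versus-regression gap is thus about 0.01 to 0.12. The matched-versus-ATE gap is 0.06 (0.300 − 0.240) to 0.36 (0.700 − 0.336).

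**Checks.** A simulation of the worked case with 100,000 JA participants and exact 1:1 matching gave:

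- matched 0.694;
- main-effects regression on everyone 0.605;
- main-effects regression on the matched pairs 0.694;
- regression with the interaction, averaged over JA participants, 0.696, and over everyone 0.392.

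Fitting on the matched pairs, or averaging over JA participants, therefore removes the gap apart from simulation error.

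**The case against.** The strongest reply is that the phrase average treatment effect is used loosely. It stands in brackets after the word outcomes, and an effect averaged over digital users is still an average effect. The matching text fixes the operational target by calling JA treated and BOA controls, and the reference to people with OA may describe only the indication. This has weight: the SAP does not formally set one estimand against another. But loose wording does not repair the problem, because no section limits the conclusion to digital users.

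It is also fair that no modifier, imbalance or eligible ratio is given in the SAP, and that a 1.0-point difference in effect between levels is as large as the equivalence margin itself. The sizes are illustrations only. The move to regression is pre-specified and has a stated reason. That justifies changing the method, but does not say that the target stays the same.

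Some stronger readings may tempt a reader and are not supported.

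- *The gap might seem largest at a 1:1 ratio* (0.20 for 70/30 with d = 1.0, 0.05 for 60/40 with d = 0.5). At 1:1, not all JA participants can be closely matched. Close pairs then weight both levels equally, as the regression does, so both give 0.500 (or 0.250) and the gap vanishes.
- *The SAP might seem to declare the regression to be the causal effect of interest.* That clause more naturally describes the adjustment set, and it names no population.
- *The subgroup sentence,* "we will be able to estimate between-group differences also in subgroups, by sex, BMI, etc"*, might seem to predict a varying effect.* It is a remark about precision. It shows only that the plan does not rest on a constant effect.
- *The sensitivity regression might seem able to overturn equivalence.* The SAP has its results presented and discussed, and gives them no part in the verdict.

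**Conclusion.** The point stands as a specification fault that should be corrected. The aim and hypothesis name a general average effect, the primary matching estimates an effect over adherent, followed-up digital users if all are closely matched, and the replacement regression has no matched sample to fix its target. Fitted with main effects on all eligible participants, it would target an overlap-weighted effect.

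The numerical size is unknown. It is zero under a constant effect and, for the sensitivity analysis, zero if the regression uses the matched pairs. The 0.01 to 0.12 point range rests on the assumed single modifier and on ratios that allow full close matching. Against a 1-point bound, it would alter the equivalence verdict only for an estimate close to that bound, and only through the missing-data switch. The larger difference between the matched effect and a population-wide average affects what the result may be said to apply to. Confidence is medium: the mismatch in the text is clear, its practical size is not.

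**What to change.** Keep matching as the primary analysis and align the rest with it.

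1. Restate the aim, hypothesis and conclusion as the average effect over digital-programme participants who meet the adherence and follow-up criteria.
2. Report how many JA participants were matched and how closely, so that readers can see whether the matched set still represents them.
3. State that the sensitivity regression either uses the matched pairs or is standardised to JA participants.
4. For the regression that replaces matching under Missing data, include programme-by-covariate terms for a short pre-named list (for example sex and BMI, which the Sample size section names for subgroups). Carry the same terms in the imputation model, and average the predictions over JA participants.

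Keeping the population-wide average as the target, with a method that estimates it, would also resolve the conflict.

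The cost is SAP wording, a few interaction terms, and a variance for the standardised estimate (for example by bootstrap). No new data are needed. The claim becomes narrower, and the regression loses a little precision.
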